The cause of obesity related HH is not well understood. Since T and androstenedione in the male can be converted to estradiol and estrone respectively through the action of aromatase in the mesenchymal cells and pre-adipocytes of adipose tissue, it has been suggested that excessive estrogen secretion due to aromatase activity in the obese may potentially suppress the hypothalamic secretion of gonadotropin releasing hormone (GnRH) (2, 8). It therefore follows that the estradiol concentrations in men with HH and obesity should be elevated to account for the suppression of gonadotropin secretion. However, we have shown that this widely believed presumption is not true (9, 10). Estradiol concentrations are lower in males with HH as compared to eugonadal obese men. This is true in men at all ages (adolescents, middle-age and elderly) (6, 9, 11). Thus, other factors associated with obesity likely account for the HH. It is now known that kisspeptin, a hypothalamic neuropeptide encoded by the *KISS1* gene, and the presence of kisspeptin receptors on the GnRH neurons (G protein-coupled receptor 54) is obligate for the release of GnRH (12, 13). Kisspeptin neurons express both leptin and insulin receptors, thus possibly accumulating evidence of metabolic health and translating it into reproductive health. Leptin appears to serve as a signal of energy reserves to regulate the hypothalamo-pituitary-gonadal axis in relation to nutritional status (14). It is possible that leptin resistance in neurons may contribute to the pathogenesis of hypogonadotropism seen in obesity. Direct evidence in humans supporting or disproving this reasoning is, however, lacking. Interestingly, the selective deletion of the insulin receptor from neurons leads to a reduction in LH and T concentrations (15). In addition, these animals have atrophic seminiferous tubules with markedly impaired or absent spermatogenesis. Incubation of hypothalamic neurons with insulin results in the facilitation of secretion of GnRH (16, 17). Thus, insulin action and insulin responsiveness in the brain are necessary for the maintenance of the functional integrity of the hypothalamo-hypophyseal-gonadal axis. A combination of leptin and insulin resistance may play a role in the pathogenesis of these defects.

Obese men with HH have more subcutaneous and visceral fat and are more insulin resistant than eugonadal obese men (4). Similarly, T concentrations in obese adolescent boys are inversely related to insulin resistance and C-reactive protein (CRP) concentrations, independent of obesity (6). We have recently shown that T replacement in middle aged men decreases fat mass, increases lean body mass and increases insulin sensitivity (4). The expression of insulin signaling genes (*IR- $\beta$* , *IRS-1*, *AKT-2*, and *GLUT4*) in adipose tissue was significantly lower in men with HH and was upregulated after T treatment. T replacement also decreased free fatty acids (FFA), CRP, Interleukin (IL)-1 $\beta$  and tumor necrosis factor (TNF)- $\alpha$  concentrations. In addition, T therapy suppressed the mRNA expression of proinflammatory mediators that inhibit insulin signaling: suppressor of cytokine signaling (SOCS)-3, inhibitor of nuclear factor kappa-B kinase (IKK)- $\beta$ , and phosphatase and tensin homolog (PTEN) in mononuclear cells (MNC). However, T therapy is not ideal for long term use in those who desire fertility since it decreases spermatogenesis (18). Therefore alternatives need to be explored for younger men. GnRH and human chorionic gonadotropin (hCG) are both effective in increasing T concentrations and increasing spermatogenesis. GnRH has to be infused continuously by an external pump while hCG therapy has to be injected subcutaneously or intramuscularly 2-3 times a week. Both are expensive for chronic long term treatment. Aromatase inhibition can suppress estradiol concentrations and increase T concentrations. However, the sharp fall in estradiol concentrations may not be ideal since males depend upon estradiol for the maintenance of their bone density and strength. Aromatase inhibitors decrease bone mineral density in elderly men (19). Clomiphene citrate is a mixture of two diastereoisomers, (cis)zuclomiphene citrate (38%) and (trans)enclomiphene citrate (62%). Zuclomiphene is thought to be an estrogen agonist in high doses (44). By contrast, enclomiphene citrate is primarily responsible for causing an increase in FSH and LH in studies of male subjects by estrogen antagonism. Enclomiphene binds potently to estrogen receptor while zuclomiphene is not believed to be active at physiological concentrations. Clomiphene is available as an oral preparation and is an estrogen antagonist at hypothalamic level. It can thus interfere with the negative feedback of estradiol. It is effective in increasing T concentrations, while maintaining spermatogenesis (18, 20). By inhibiting the normal estrogen mediated feedback, enclomiphene has been shown to increase T concentrations in obese men with HH, even though they do not have elevated estradiol concentrations (18). Clomiphene increases bone density and does not affect lipid profile (21). In a randomized placebo controlled cross over trial, Pelusi et al randomized 24 obese men (age range 35-55 years, mean 47 years) with diabetes or prediabetes and low total testosterone (<300 ng/dl) to clomiphene 25mg or placebo capsules daily (22). There were two periods of treatment (3 months each) separated by a washout of 6 weeks. Treatment with clomiphene doubled the calculated free testosterone concentrations (7.5 ng/dl to 15 ng/dl). LH,

FSH and free estradiol also doubled. Bendre et al noted similar results in a retrospective chart review of obese young men (18-21 years) with low total testosterone (<350 ng/dl) after treatment with clomiphene(23). Clomiphene is not FDA approved for treatment of hypogonadism, but it may be an attractive and inexpensive alternative to T therapy in young men who are interested in fertility.

Some (but not all) studies have shown that BMI is inversely related to sperm counts, sperm morphology and sperm motility(24-29). Data are most consistent about the impact of morbid obesity on spermatogenesis. In a meta-analysis of 21 studies, BMI>40kg/m^2 was associated with a doubling of risk of oligospermia (<40 million spermatozoa per ejaculate) or azoospermia (30). Weight loss in obese males increases sperm count (31). Obese males have evidence of decreased testicular function, as shown by lower concentrations of insulin like factor 3 (sensitive marker of Leydig cell function) and inhibin B (marker of Sertoli cell function) (32-34). A longitudinal study of testicular function across childhood has shown that weight gain during childhood is associated with lower testicular volume, serum T and inhibin B concentrations at the age of 21 years(35).

We **hypothesize** that 1) obese young males with HH (18-45 years of age) will show evidence of decreased Leydig and Sertoli cell function, decreased insulin sensitivity and increased inflammation; and 2) Clomiphene treatment will reverse these abnormalities.

**Aim 1.1:** To compare the serum concentrations of insulin like factor 3 (sensitive marker of leydig cell function) and inhibin B (marker of Sertoli cell function) in obese males with and without HH and in lean males.

**Aim 1.2:** To compare the insulin resistance (measured by homeostatic model assessment-insulin resistance (HOMA-IR) in obese males with and without HH and in lean males.

**Aim 1.3:** To compare FFA, TNF- $\alpha$ , IL-1 $\beta$  and CRP concentrations, and mRNA expression of SOCS-3, IKK- $\beta$ , and PTEN in MNC in obese males with and without HH and in lean males.

**Aim 2.1:** To measure the change in serum concentrations of T (**primary endpoint**), insulin like factor 3 and inhibin B after treatment with clomiphene tablets or placebo for 12 weeks in obese males with HH.

**Aim 2.2:** To measure the change in waist circumference and HOMA-IR in obese males with HH after treatment with clomiphene or placebo for 12 weeks in obese males with HH.

**Aim 2.3:** To measure FFA, TNF- $\alpha$ , IL-1 $\beta$  and CRP concentrations, and mRNA expression of SOCS-3, IKK- $\beta$ , and PTEN in MNC in obese males with HH after treatment with clomiphene or placebo for 12 weeks in obese males with HH.

## **Significance**

The prevalence of obesity in adolescents has seen a steep rise in the last few decades. 20% of all adolescent boys are now considered obese (BMI  $\geq$ 95th percentile)(36). However, the consequences of the lower FT at completion of puberty in obese boys are not known. Males are supposed to achieve their “peak T concentrations” at puberty. Thereafter, there is a decline of FT at the rate of 2% per year for the rest of life (37). It is possible that HH in obese young males with HH have more insulin resistance, inflammation and possibly increased predisposition to diabetes and cardiovascular diseases. They may also have deficient spermatogenesis and decreased fertility. It is the intent of this project to understand the effects of having HH in obese young men on testicular function, insulin sensitivity and inflammation. This study will also generate preliminary efficacy data on a therapeutic option (clomiphene) for this condition. The results will inform the design of future trials and provide a comparison for other treatment modalities to increase T concentrations in young males with HH.

## **APPROACH**

The study will be conducted at the division of Endocrinology, Saint Louis University. Young males between the ages of 18-45 years will be recruited for the study. A total of 90 males will be recruited: 30 obese males (defined as  $\geq$ 30 kg/m^2) with HH, 30 obese males with normal FT concentrations and 30 lean males (<25 kg/m^2) with normal FT concentrations.

**Hypogonadal males:** 30 male subjects with HH will be recruited into the study. HH will be defined as subnormal FT concentrations along with normal or low LH concentrations ( $\leq$ 10 IU/L). We will define subnormal FT as <6.5 ng/dl. Subjects with subnormal FT and high LH (>10 IU/L) will not be recruited into the study. Obese subjects will be randomized to receive clomiphene or placebo (15 subjects each) thrice a week for 12 weeks.

**Eugonadal men:** 30 obese and 30 lean males with normal FT ( $\geq$ 6.5 ng/dl) will also be recruited in the study to serve as comparison groups. They will not be treated clomiphene.

**INCLUSION CRITERIA FOR THE STUDY:** Males with age 18-45 years inclusive will be recruited. Subjects with type 2 diabetes on anti-hyperglycemic drugs (including insulin) will be allowed as long as they are on stable doses of these compounds for at least 6 weeks. The doses of anti-hyperglycemic can be changed if the subject has hypoglycemia or hyperglycemia. A record of all the changes in the doses of the anti-diabetic drugs will be kept.

**EXCLUSION CRITERIA FOR THE STUDY:** 1) Use of androgens, clomiphene, hCG, aromatase inhibitors or over the counter health supplements which contain androgens currently or in the past 6 months; 2) Hematocrit > 50%; 3) Congestive heart failure; 4) currently suffering from depression; 5) type 1 diabetes; 6) Hepatic disease (transaminase > 3 times normal) or cirrhosis, or a history of liver dysfunction; 7) Renal impairment (eGFR < 30 ml/min/1.73m^2); 8) HIV or Hepatitis C positive status; 9) Participation in any other concurrent clinical trial; 10) currently suffering from foot ulcer, significant periodontal disease or any other chronic infectious condition 11) known allergy to clomiphene 12) uncontrolled adrenal or thyroid dysfunction 13) presence of an organic intracranial lesion e.g. pituitary tumor 14) history of cataracts 15) history of venous thromboembolic disease (i.e. deep vein thrombosis or pulmonary embolism).

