### **STUDY DESIGN:-**

**Screening Day (part of study):** All subjects will have completed the following procedures prior to participating in the study:-

1) Medical History; 2) Physical Exam: testicular volume will be measured by an orchidometer (38); 3) Informed consent; 4) Baseline lab (30 ml) draw to measure CBC, comprehensive metabolic panel (CMP that includes liver and kidney function tests), total and free T, SHBG, LH and FSH. All labs will be drawn in the fasting state in the morning before 10am. All laboratory samples will be tested in the Endocrine laboratory in Doisy Hall Room 204.

**Study visits for males with normal FT:** The participants will come fasting and have blood drawn for research labs (insulin, glucose, inflammation). They will then be discharged from the study.

**Study visits for obese males with HH:** These subjects will enter a double blind randomized placebo controlled trial. Subjects who qualify and consent to take part in the study will be assigned a number by a computerized random number generation program and will be randomized (1:1) to receive either clomiphene or placebo. An unblinded research nurse and pharmacist will administer study product, all other investigators and the study participants will be blinded. This number will be used as the study subject ID. A master list of subject name and study ID will be kept under lock and key to protect patient identifiers. Only the assigned research nurse will have access to the randomization list.

**1. Visit day 0:** The participants will come fasting and have blood drawn for research labs (insulin, glucose, CRP; 45 ml). Waist circumference will be measured. They will be given a supply of clomiphene or placebo pills containing cellulose. Clomiphene citrate is available as 50 mg tablets and has a half life of 5-7 days. The starting dose of clomiphene will be 25mg on Monday, Wednesday and Friday mornings. All subjects will be given a pill container that will have separate boxes for different days of the week.

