**2. Visits to adjust study drug (week 4 and week 8):** A blood sample (30 ml) will be collected at weeks 4 and 8 to measure CBC, CMP and FT concentrations. The time frame for follow-ups will be within a week of the designated follow up time. Dose of clomiphene will be adjusted to keep FT between 12 and 16 ng/dL (mid-normal for healthy young men). If FT is <12 ng/dl, then the dose of CC will be increased by 25mg/week. If FT is >16 ng/dl, then the dose will be reduced by 25mg/week. The blood samples for dose adjustment will be taken on Wednesday or Friday. Patients in both clomiphene and placebo groups will be told that their tablet quantities may vary during the study. If the number of pills of a patient in the clomiphene group is changed, a similar change will be made in the number of placebo tablets in the next patient in placebo group.

**3. Week 12:** The participants will come fasting and have blood drawn for research labs, CBC, CMP, SHBG, LH, FSH total and free T (45 ml). Waist circumference and testicular size will be measured. Gynecomastia will be assessed. Subjects will then be discharged from the study.

The following study termination criteria will be applied:-

- Adverse events considered by the PI to be associated with the use of the study drug
- Suspected thromboembolic event, including pulmonary embolism. Subjects who have a thromboembolic event ruled out may reinstate treatment
- Hemoglobin of 18 g/dL or higher, or a hematocrit of 54% or higher
- Visual changes which may be prolonged and possibly irreversible. Subjects will be advised to stop drug and be referred to an ophthalmologist.
- The subject requests to be withdrawn from the study

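### The LH limit of 10 IU/L applies only to men with low FT, so high-LH men can enter the comparison groups and shrink the baseline INSL3 difference in Aim 1.1

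*Combined protocol and SAP*

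**What the plan says.** APPROACH sets the group definitions. For the HH group, "HH will be defined as subnormal FT concentrations along with normal or low LH concentrations", with FT below 6.5 ng/dl and LH at or below 10 IU/L. The matching refusal reads "Subjects with subnormal FT and high LH (>10 IU/L) will not be recruited into the study".

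For the other two groups, "30 obese and 30 lean males with normal FT" (6.5 ng/dl or more) "will also be recruited in the study to serve as comparison groups". BMI class separates the two. No LH or FSH value appears in their definition.

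The list of 15 exclusion criteria covers an organic intracranial lesion such as a pituitary tumor. It names no gonadotropin level and no primary testicular disease.

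Under STUDY DESIGN, the screening blood draw for all subjects includes "total and free T, SHBG, LH and FSH", and testicular volume is measured. FSH has no stated role in eligibility, grouping, endpoints or analysis.

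These three groups feed Aim 1.1, which reads: "To compare the serum concentrations of insulin like factor 3 (sensitive marker of leydig cell function) and inhibin B (marker of Sertoli cell function"). The contrasts are between HH men, obese comparison men and lean comparison men.

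**The concern.** The plan treats LH above 10 IU/L as disqualifying at an FT just under the cut-off and ignores it at an FT just over. A man with FT 6.4 ng/dl and LH 12 IU/L is refused. A man with FT 6.6 ng/dl and the same LH can join the reference group for Leydig cell function.

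If the second man's FT is being sustained by raised LH, his Leydig cells may be impaired although his FT is in range. INSL3 is the marker the plan chose to detect that. This reading is a physiological assumption; the documents do not state it. Granting it, such men pull the reference INSL3 mean toward the HH mean, and Aim 1.1 understates the deficit it was designed to find.

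The missing exclusion for known primary testicular disease is a related gap. It applies to all three groups, although testicular function is what Aim 1.1 measures.

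**Working it through.** **1. The plan's own figures.** Data Analysis gives no sample size, mean or SD for INSL3 or inhibin B, so there is no stated figure to reproduce for this comparison. The two sizings it does give are as follows (t-test, two-sided 5% and 80% power; two-sided is assumed).

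- FT: 50/40 = 1.25 SD needs 12 evaluable men per arm, and 12/(1 − 0.20) = 15. This matches the plan.
- HOMA-IR: 20/25 = 0.8 SD needs 26 per group. The planned 30 gives 86% power, so the plan is on the safe side.

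Neither depends on the LH rule.

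**2. The entry rules side by side.**

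| FT (ng/dl) | LH (IU/L) | Outcome under APPROACH |
|---|---|---|
| < 6.5 | ≤ 10 | HH group, if obese |
| < 6.5 | > 10 | refused |
| ≥ 6.5 | ≤ 10 | comparison group by BMI |
| ≥ 6.5 | > 10 | comparison group by BMI |

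Only the last row is at issue. The selection on LH is one-sided in the contrast of HH men with either comparison group. It is not one-sided between obese and lean comparison men, since neither is restricted.

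**3. Dilution of the difference.** Suppose k of 30 comparators have INSL3 at the HH mean. The reference mean becomes (1 − k/30) × eugonadal mean + (k/30) × HH mean, so the observed difference is (1 − k/30) times the true one.

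- k = 1: loss of 1/30 = 3.3%
- k = 2: loss of 2/30 = 6.7%
- k = 3: loss of 3/30 = 10%

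The values of k are assumptions.

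**4. Illustration of power.** Assume a true difference of 0.8 SD (the same ratio as the plan's HOMA-IR sizing) and 30 per group. Let a share f of the comparators have a marker m = 1 to 2 SD lower. Then:

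- difference = 0.8 − f × m
- comparator variance = 1 + f(1 − f)m²
- pooled SD = √[(1 + comparator variance)/2]

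Example, f = 0.10 and m = 2: difference 0.8 − 0.2 = 0.60; variance 1 + 0.09 × 4 = 1.36; pooled SD √1.18 = 1.086; standardized difference 0.60/1.086 = 0.55; power 56%.

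| Share f | Expected men of 30 | Difference (SD), m = 1 to 2 | Power |
|---|---|---|---|
| 0 | 0 | 0.80 | 86% |
| 2% | 0.6 | 0.78 to 0.76 | 84 to 81% |
| 5% | 1.5 | 0.75 to 0.70 | 81 to 72% |
| 10% | 3 | 0.70 to 0.60 | 74 to 56% |

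These rows are harsher than step 3, because a marker 1 to 2 SD lower lies below the HH mean, which is 0.8 SD lower. With HH-like values the difference at k = 3 would be 0.8 × 0.90 = 0.72 SD.

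**The case against.** **Size.** The documents give no share of men with FT in range and raised LH. The 3 to 10% follows directly from the assumed count, and at a 2% share the loss is minor. This stands. A reader might infer that such men will enter and will distort Aim 1.1; the documents support only that they can.

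**Definition.** The plan defines its comparison men by FT, so this is a gap and not an internal contradiction. INSL3 and inhibin B have no sample size and are not among the listed secondary endpoints, and the Significance section calls the efficacy data preliminary. This also stands and limits the priority.

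**Selecting on the outcome.** Gonadotropins are related to the markers being compared, so limiting them could itself alter Aim 1.1, and stricter comparators could enlarge the HH difference. For LH the objection is weak: the limit already applies to the HH group, and extending it makes selection symmetric. For FSH it is strong. A reader might conclude that raised FSH should also bar entry, since a man with LH at or below 10 IU/L and raised FSH can be classed as HH. But FSH is closely tied to inhibin B, and an FSH limit could remove the Sertoli cell deficit that the plan's first hypothesis predicts. The documents do not support that step.

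**The randomized part.** A reader might extend the concern to Aim 2.1. Men with LH above 10 IU/L cannot be in the HH group, and allocation is randomized 1:1, so any raised-FSH men there do not bias clomiphene against placebo. At most they dilute an inhibin B response, by an amount the documents do not allow one to calculate.

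**Conclusion.** The concern holds for the baseline comparison in Aim 1.1. The LH limit clears high-LH men from the HH group and leaves them eligible for both reference groups, and known primary testicular disease is excluded nowhere. The likely direction is an understated INSL3 difference between HH men and comparators. The size is about 3 to 10% if 1 to 3 of 30 comparators have HH-like INSL3, and small if such men are rare. That range rests on an assumed count and on the assumption that high LH with FT in range goes with low INSL3; the documents supply neither. The primary FT endpoint, its sample size and the between-arm comparison in Aim 2.1 are unaffected. The change is worth making because it is cheap, not because distortion has been shown.

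**What to change.** In APPROACH, apply the existing limit of LH at or below 10 IU/L to all three groups, and add known primary testicular disease to the exclusion criteria. LH, medical history and testicular examination are already part of screening, so the cost is one or two sentences and a few extra screen failures. Recording how many men are refused on LH in each group would show how much the rule matters.

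Do not add an FSH entry limit. In Data Analysis, state that screening LH and FSH will be reported by group, and that the INSL3 and inhibin B comparisons will be repeated without men whose FSH is above the laboratory's reference limit, as a sensitivity analysis. This needs no new data. If enrolment is too advanced to change eligibility, the same approach can be used for comparators with LH above 10 IU/L.

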**Data Analysis:** The focus of the proposed research is to evaluate the efficacy of clomiphene treatment on T concentrations in young obese post-pubertal males. Transformations of the data in order to meet statistical assumptions may be considered. The results will be computed as mean  $\pm$  standard deviation (SD). The primary endpoint of the study is to detect a difference in FT concentrations after treatment with clomiphene for 12 weeks. There are no prior studies analyzing the effect of clomiphene in young males with HH. However, studies in middle aged men with obesity related HH and use of clomiphene or its isomer, enclomiphene have shown an increase in FT concentrations by 150%(21, 43). Change in FT concentrations following clomiphene or placebo for 12 weeks will be compared among the groups by unpaired *t*-test. Conservatively estimating a difference in FT concentrations of 50%, a sample size of 15 patients per treatment group (assuming a drop-out rate of 20%) should provide adequate power( $\beta = 0.8$ ) to detect a significant difference ( $\alpha = 0.05$ ), provided the standard deviation of the residuals is not greater than 40%. Thus 30 obese subjects with HH (15 patients each in clomiphene and placebo groups) will be sufficient. For baseline comparisons with men without HH, we will recruit 30 eugonadal obese and 30 lean males. Thus there will be 90 subjects in the study.

**Secondary End Points:** The secondary endpoints for the study will be comparison of the relative change from baseline in HOMA-IR and inflammatory mediators after clomiphene or placebo. These parameters will also be compared between obese and lean males at baseline. We have previously shown that obese men with HH have 36% higher insulin resistance than eugonadal men. Estimating a difference in HOMA-IR of 20%, a sample size of 30 patients per treatment group should provide adequate power( $\beta = 0.8$ ) to detect a significant difference ( $\alpha = 0.05$ ), provided the standard deviation of the residuals is not greater than 25%.

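### The non-randomised Aim 1 comparisons are open to confounding by age: HH men are likely to be older than the eugonadal obese men, and the plan neither balances nor adjusts for age

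*Combined protocol and SAP*

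**What the plan says.** - **Aims 1.1 to 1.3** compare INSL3, inhibin B, HOMA-IR and inflammatory markers "in obese males with and without HH and in lean males". These comparisons test the first hypothesis, that HH goes with poorer testicular function, lower insulin sensitivity and more inflammation.
- **Approach, inclusion criteria:** "Males with age 18-45 years inclusive will be recruited".
- **Approach, hypogonadal males:** "We will define subnormal FT as <6.5 ng/dl", with LH no higher than 10 IU/L. The cut-off does not vary with age.
- **Approach, eugonadal men:** "30 obese and 30 lean males with normal FT" form the comparators; the plan says that they "will also be recruited in the study to serve as comparison groups". Beyond the common eligibility criteria, only BMI and FT define them.
- **Significance:** after puberty "there is a decline of FT at the rate of 2% per year for the rest of life".
- **Data Analysis:** "For baseline comparisons with men without HH, we will recruit 30 eugonadal obese and 30 lean males". No test or covariate is named for the three-group comparison. The unpaired t-test is specified for the change in FT between the randomised arms.

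Approach, Study Design and Data Analysis contain no age matching, age strata, age quota or age adjustment.

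**The concern.** A fixed threshold on a quantity that falls with age tends to place older men below it and younger men above it. The plan supplies both halves of that mechanism: the 2% annual decline and the single cut-off. Aim 1 is not randomised, so nothing in the design offsets the tilt. If INSL3, inhibin B, HOMA-IR or the inflammatory markers also change with age, part of any difference between HH and comparison men would be an age effect read as an HH effect. What is at stake is the interpretation of the first hypothesis.

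**Working it through.** **1. The plan's own figure.** The only sample-size statement that bears on Aim 1 is for HOMA-IR: 30 per group, difference 20%, SD 25%, alpha 0.05 (two-sided assumed), power 0.8. I apply it to the baseline groups, which are the groups of 30.

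n = 2 × (1.96 + 0.842)² × (25/20)² = 24.5, so 25 per group (26 with the t-test). Power with 30 per group is 0.86 by t-test. The figure of 30 is adequate on these inputs if the groups differ only in HH status.

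**2. FT decline over the eligible range.** 0.98^(45 − 18) = 0.98^27 = 0.58, a 42% fall. The age at which a man reaches 6.5 ng/dl is 18 + ln(6.5/FT at 18)/ln(0.98):

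| FT at 18 (ng/dl) | Age at crossing 6.5 |
|---|---|
| 8 | 28 |
| 9 | 34 |
| 10 | 39 |
| 11 | 44 |

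On the plan's premise, the same man can be eugonadal early in the age range and HH late in it.

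**3. Expected age gap, HH minus eugonadal obese (simulation).** Assumptions, none given in the documents: log-normal FT, median 7 to 10 ng/dl at age 31.5, between-man CV 25% to 45%, and the same source age distribution for both groups. The 2% decline and the 6.5 cut-off are the plan's.

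| Assumed ages of screened men | Gap in mean age (years) |
|---|---|
| Uniform, 18 to 45 | 4.4 to 8.0 |
| Skewed young (beta 1.5, 3) | 2.3 to 5.9 |
| Skewed old (beta 3, 1.5) | about 2 to 3.7 |
| Clustered at 31.5, SD 4 | 1.2 to 2.7 |

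The 8.0 comes from the case in which only 7% of screened men are HH. A wider grid (median 6.5 to 10 ng/dl at age 30, CV 20% to 50%) gives about 1 to 9 years. On that grid the chance that 30 HH men are on average older than 30 eugonadal men is 84% to more than 99%.

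**4. Lean men.** The dose-adjustment section treats 12 to 16 ng/dl as the middle of the range in healthy young men. With an assumed lean median of 14 ng/dl, CV 25% to 45% and uniform ages, the cut-off excludes 0.4% to 4.7% of lean men and moves their mean age by 0.04 to 0.26 years. Any HH-lean gap therefore comes from the HH side: about 2.5 to 7.4 years with uniform ages, if lean men keep the source mean of 31.5.

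**5. What a gap would do to HOMA-IR.** Spurious difference = age slope × gap. The documents give no slope, so these slopes are assumptions. The standard error is 25 × √(2/30) = 6.45 points. Two-sided t-test at 0.05, 30 per group:

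| Example (slope × gap) | Spurious difference (points) | False-positive rate |
|---|---|---|
| 0.25%/yr × 4 yr | 1 | 5.3% |
| 0.5%/yr × 4 yr | 2 | 6.1% |
| 1%/yr × 4 yr | 4 | 9.4% |
| 1%/yr × 8 yr | 8 | 23% |

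**6. Price of adjusting.** With age SD 7.8 (uniform ages), the squared correlation between group and age is about 0.25 × gap²/7.8², and the effective n is 30 × (1 − that value). The residual SD is kept at 25%.

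| Gap (years) | Effective n per group | Power for 20% |
|---|---|---|
| 0 | 30 | 0.86 |
| 4.0 | 28.0 | 0.84 |
| 6.2 | 25.3 | 0.80 |
| 8.3 | 21.5 | 0.73 |

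**The case against.** The strongest reply is that the documents give no expected age for any group. The three groups are filled separately to 30 each, so the realised ages depend on who volunteers, and the gap could be small or absent. That stands: the tilt is an expectation, and its size depends heavily on the assumed age mix.

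Two further points also stand. A reader might infer that the rule sorts younger men into both comparison groups. It does so for the obese men, but step 4 shows almost no effect on the lean men. A reader might also take slopes of 1% to 2% per year over 4 to 8 years and conclude that HOMA-IR would show a spurious difference of 4% to 16%, close to the planned 20%. The documents give no slope for any marker, and at 0.25% to 0.5% per year over 4 years the false-positive rate is barely above 5%.

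Finally, the stated focus of the research is the effect of clomiphene on testosterone, which is assessed between randomised arms. This limits the reach of the point but does not remove it: Aim 1 carries its own hypothesis and accounts for 60 of the 90 men.

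**Conclusion.** The point holds as a gap in the Aim 1 analysis. On the plan's own premises HH men are likely to be older than eugonadal obese men, by roughly 1 to 8 years under the stated assumptions on FT level, FT spread and age mix, and nothing planned would balance or remove the difference. The resulting bias could be negligible or material. The documents do not allow it to be sized for any marker.

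Three stronger readings are not supported. The documents do not establish that HH men will be older. The single 6.5 ng/dl cut-off is not itself an error; the gap is the absence of matching or adjustment. The primary endpoint and the rest of Aim 2 are not affected, because those comparisons are randomised within the HH group.

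This is a cheap improvement to the plan, not a flaw in its main comparison.

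**What to change.** In Data Analysis, state that the Aim 1 group comparisons use a linear model (ANCOVA) with group as factor and age as covariate, on a transformed scale where needed, and report age by group. Age is known at screening, so no new data are required. The cost is one degree of freedom and the loss of precision in step 6: little at a 4-year gap, but HOMA-IR power falls to about 0.73 at 8.3 years.

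Where feasible, also balance age while filling the two eugonadal groups, which limits that loss. This is not free. An obese man's group is known only once his screening FT returns, so some men who have already consented and given blood would be turned away. The age mix of the HH group is also unknown in advance, so targets would have to be updated as it fills. Balancing in broad age bands would leave some residual gap, so the covariate should stay in the model either way.
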